11.2.3 Vaccination Site Reactogenicity Assessment

All subjects will undergo a vaccination site reactogenicity assessment (injection site pain, redness, swelling, and itching) at 1 hour after the vaccination on the day of vaccination (Day 1, Day 8 [Rabipur Dose 2], and Day 29 [Rabipur and Groups 3a and 4a]) and 1 or 2 days after each vaccination (Day 2 or 3, Day 10 [Rabipur], and Day 30 or 31 [Rabipur and Groups 3a and 4a]). Note that Days 3 and 31 were planned in the original protocol and only apply to subjects in Groups 1 and 2 who were already enrolled and vaccinated before the last protocol amendment was issued. Days 2 and 30 apply to all other subjects.

Local reactions will be assessed by the investigator on an intensity scale of absent, mild, moderate, and severe. Direct data entries of mm for redness and swelling and °C for fever/temperature will be given and mapped to intensity grading the same way as done for solicited local AEs.

The vaccination site reactogenicity assessment will be displayed for any symptom and for the individual terms by vaccination group for any vaccination dose and by vaccination dose (number).

Tabulations will also display frequencies and percentages by grade (intensity). Symptoms, that are documented on the day of vaccination and on 1 or 2 days after vaccination are counted only once per vaccination with highest grade.

11.3 Extent of Exposure

Subjects shall receive 1 or 2 vaccination doses of CV7202 or 3 vaccination doses of Rabipur. All data referring to the Vaccination section of the eCRF will be listed.

All visit dates will be listed. Time between visits as well as total trial duration will be derived and tabulated with descriptive statistics (duration of total trial [days] = date of trial completion or discontinuation – date of first informed consent + 1).

11.4 Physical Examination, Weight, BMI

Physical examination results will be included in data listings only. Weight and BMI will be summarized using descriptive statistics at baseline and at each postbaseline time point. BMI will be derived for post vaccination visits if not collected on the CRF and weight available at that visit. BMI will be derived as follows: weight (kg)/height (m)².

11.5 Vital Signs

Vital signs will be summarized using descriptive statistics at baseline and at each postbaseline visit.

11.6 Electrocardiogram

Overall interpretation of electrocardiogram results will be displayed in a listing.

11.7 Safety Laboratory Evaluation

Laboratory parameters (hematology, biochemistry, and coagulation) will be summarized using descriptive statistics at baseline and at each postbaseline time point. The categorization into low-normal-high (below lower reference range/ within reference range/ above upper reference range) will also be summarized. In summary tables, results below or above the detection limit are set to the detection limit.

11.8 Pregnancy Test Results

Results of serum pregnancy tests and urine dipstick pregnancy tests will be displayed in listings.

12. CHANGES TO PROTOCOL-SPECIFIED ANALYSES

The protocol defines 2 PP sets as subsets of the FA set. Due to the small number of subjects per treatment group, it was decided that no per-protocol sets will be defined and used for analysis.

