8.9 Concomitant Therapy and Vaccines

Concomitant medication and vaccines must be recorded in the subject's eCRF.

If post-exposure vaccination for rabies is needed, the subject should be discontinued from receiving a further trial dose, but followed-up for safety assessments.

For additional information, refer to section 6.2.

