9.3 Immunogenicity Assessments

The following immunogenicity assessments will be made:

Rabies-specific serum VNTs will be measured using the WHO-recommended rapid fluorescent foci inhibition test (RFFIT) before and after vaccination on Days 1, 8, 15, 29, 36, 43, 57, 91, and 6, 12, 18 and 24 months post-last dose.

The percentages of vaccine recipients with VNTs ≥ 0.5 IU/ml (WHO-recommended threshold correlating with protective immune responses) will be determined for each trial group. An antibody titer of 0.5 IU/ml serum is viewed as a surrogate of protection and defines seroconversion [26]. GMTs by treatment group will be calculated based on the VNTs on Days 1, 8, 15, 29, 36, 43, 57, 91, and 6, 12, 18 and 24 months post-last dose. VNTs assessments will be performed in a GCP-compliant laboratory.

Note that VNTs assessments at 18 and 24 months after the last vaccination will only be performed in subjects with detectable RABV-G-specific IgG at 6 months after the last vaccination or Day 91 if the Month 6 blood sample is not available.

RABV-G-specific IgM, IgG and IgA serum antibody levels will be measured by enzyme-linked immunosorbent assay (ELISA) on Days 1, 8, 15, 29, 36, 43, 57, 91, and 6 and 12 months post-last dose. In addition, RABV-G-specific IgG serum antibody levels will be measured at 18 and 24 months after the last vaccination in subjects with detectable RABV-G-specific IgG at 6 months after the last vaccination or Day 91 if the Month 6 blood sample is not available.

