10.2 Populations for Analyses

Safety set: This is the subset of subjects, who have received at least one dose of the candidate rabies mRNA vaccine CV7202 or the active control Rabipur® and for whom any post-Day 1 safety data are available. The statement that a subject had no AEs (on the Adverse Event eCRF) constitutes a valid safety assessment. The analysis of safety will be performed on this population.

Full-analysis (FA) set: This is the subset of the Safety Set with subjects who have the baseline sample and at least one additional blood sample available for VNT analysis. This analysis set is the primary analysis set for all immunogenicity objectives.

Per protocol (PP) set: This is defined as a subset of the FA set as follows:

1. PP1 = Subjects enrolled in Group 1 (Rabipur®) and Groups 2 to 4 who have received at least 1 administration of the trial product (including those to be selected for the second vaccination), have completed the Day 57 visit and for whom baseline through Day 57 immunological results (at least rabies VNTs) are available.
2. PP2 = Defined as a subset of PP1 comprised of subjects who have received two administrations of the trial product, have completed the Day 91 visit and for whom baseline through Day 91 immunological results (at least rabies VNTs) are available.

Any subject for whom substantive protocol deviations are documented will be excluded from the PP set. The following pre-defined major protocol deviations will lead to the exclusion from the PP set:

- Any deviation of the Inclusion/Exclusion criteria.
- Any trial subject that requires therapy listed as an exclusion criterion in section 6.2.
- Any trial subject that has not received the trial product on the scheduled date.
- Any trial subject for whom the immunological sample has been taken outside of the planned visit window.
- Pre-existing RABV-G specific immune response.

Further subgroup analyses may be defined and specified in the statistical analysis plan (SAP).

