8. ANALYSIS SETS

The following subject population will be used for safety analyses:

- **Safety analysis set** will include all subjects who have received at least 1 dose of the candidate rabies mRNA vaccine CV7202 or the active control Rabipur and for whom any post-Day 1 safety data are available. The statement that a subject had no AEs (on the Adverse Event eCRF) constitutes a valid safety assessment. The analysis of safety will be performed on this population.

The following subject populations will be used for analyses of immunogenicity objectives:

- **Full analysis (FA) set** is the subset of the safety analysis set with subjects who have the baseline sample and at least 1 additional blood sample available for VNT analysis. This analysis set is the primary analysis set for all immunogenicity objectives.

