10.2 Secondary Immunogenicity Analysis

The number and percentage of subjects with Rabies Specific serum VNTs ≥ 0.5 IU/ml will be determined for each visit and displayed by vaccination group and dose regimen including 95% exact confidence limits. The percentages will be based on subjects providing data for the respective visit.

For evaluation of values below the limit of quantification (=BLQ values) for tables and figures, the following conventions will be made:

- Values <0.1 are identified as BLQ values.
- All concentration values marked as BLQ will be set to $0.5 * \text{LLOQ}$ (= 0.1 IU/ml) = 0.05 IU/ml
- Missing post-dose values will not be replaced.

Absolute (raw untransformed) serum VNT values will be summarized for each visit by vaccination group and dose regimen.

Serum VNT values will be log-transformed and the mean, SD and 95% confidence interval of the log-transformed values will be calculated. The serum GMTs (= antilog mean of log-transformed data) and the corresponding 95% confidence intervals for the GMTs (=antilog lower and upper 95% confidence bound of log-transformed data) as well as geometric SD, median, minimum and maximum will be tabulated by vaccination group and dose regimen for baseline and each postbaseline visit.

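### With the per-protocol sets dropped, no planned analysis sets aside rabies titers that predate the trial vaccine or follow non-trial rabies vaccine or immunoglobulin

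*SAP*

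**What the plan says.** **Protocol.** Section 10.2 makes the FA set primary: "This analysis set is the primary analysis set for all immunogenicity objectives". It then defines two PP sets and lists major deviations that exclude a subject from them. Two matter here: "Pre-existing RABV-G specific immune response" and "Any trial subject that requires therapy listed as an exclusion criterion in section 6.2". Section 9.3 says that a titer of 0.5 IU/ml "is viewed as a surrogate of protection and defines seroconversion". Section 8.9 foresees rabies vaccination outside the trial: "If post-exposure vaccination for rabies is needed, the subject should be discontinued from receiving a further trial dose", with safety follow-up continuing.

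**SAP.** Section 12 cites small groups and says that "it was decided that no per-protocol sets will be defined and used for analysis". Immunogenicity is then analysed only in the FA set, which section 8 defines as safety-set "subjects who have the baseline sample and at least 1 additional blood sample available for VNT analysis". For the proportion with VNT of at least 0.5 IU/ml, section 10.2 says: "The percentages will be based on subjects providing data for the respective visit". Section 6.5 plans no subgroup analysis beyond dose regimen. Section 9.2 leaves the impact of deviations to a data review meeting. The programming note to listing 16.2.3.1 names a major protocol deviation as a possible reason for exclusion from the analysis set.

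**The concern.** The two VNT secondary endpoints, the percentage at or above 0.5 IU/ml and the geometric mean titer (GMT), will be read as the response to CV7202 by dose and number of doses. A titer that the trial vaccine did not cause raises both.

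There are two routes. First, no rabies serology is among the entry criteria (Protocol 6.1 and 6.2), and the baseline VNT is drawn on Day 1. Unrecognised prior immunity therefore becomes known only from that sample. Second, rabies vaccine or immunoglobulin may be given outside the trial during two years of follow-up. The protocol treated pre-existing immunity, and therapy on its exclusion list, as reasons to leave the PP sets. No analysis in the SAP now does this.

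The reason given for dropping the PP sets also cuts the other way. In small groups, a single unrelated titer weighs most.

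**Working it through.** **1. Group sizes.** SAP 6.4 reports 53 subjects vaccinated: 16 (1 µg) + 16 (2 µg) + 10 (5 µg) + 11 (Rabipur) = 53, which agrees. The planned total is 10 + 10 + 16 + 16 = 52 (Protocol 8.4). Each one- or two-dose regimen at 1 and 2 µg has 8 subjects (Protocol 8.5).

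**2. Tracing an affected subject through the rules.**
- FA membership (SAP 8): a baseline and one later VNT sample suffice, so the subject is in.
- Denominator (SAP 10.2): everyone with a result at the visit, so the subject is counted.
- Numerator: any titer at or above 0.5 IU/ml. No rise from Day 1 is required, so the subject scores Yes while the titer stays that high.
- Exclusion, censoring or sensitivity rule in the SAP: none.

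**3. Effect on the percentage.** Let one of n subjects be affected and r of the other n − 1 respond. The planned table shows (r + 1)/n. Without that subject it shows r/(n − 1). The difference is

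(r + 1)/n − r/(n − 1) = (n − 1 − r) / [n(n − 1)].

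Exact Clopper-Pearson 95% limits, the SAP's method, are in brackets.

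| n | r | As planned | Subject removed | Difference (points) |
|---|---|---|---|---|
| 8 | 0 | 1/8 = 12.5% (0.3–52.7) | 0/7 = 0% (0–41.0) | 12.5 |
| 8 | 4 | 5/8 = 62.5% (24.5–91.5) | 4/7 = 57.1% (18.4–90.1) | 3/56 = 5.4 |
| 10 | 0 | 1/10 = 10.0% (0.3–44.5) | 0/9 = 0% (0–33.6) | 10.0 |
| 10 | 5 | 6/10 = 60.0% (26.2–87.8) | 5/9 = 55.6% (21.2–86.3) | 4/90 = 4.4 |
| 16 | 0 | 1/16 = 6.3% (0.2–30.2) | 0/15 = 0% (0–21.8) | 6.3 |
| 16 | 8 | 9/16 = 56.3% (29.9–80.2) | 8/15 = 53.3% (26.6–78.7) | 7/240 = 2.9 |

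The difference shrinks as the others' response rises, and is zero if they all respond (r = n − 1).

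**4. Effect on the GMT, with assumed titers.** Suppose all other subjects are below quantification, which SAP 10.2 sets to 0.05 IU/ml, and the affected subject has titer t. The GMT is multiplied by (t/0.05)^(1/n). For t from 0.5 to 10 IU/ml this is 1.33 to 1.94 at n = 8, 1.26 to 1.70 at n = 10, and 1.15 to 1.39 at n = 16. The documents give no such titers. The factor is smaller when the others have measurable responses below t.

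**The case against.** The strongest reply is that SAP 12 changes nothing in the main result. A reader might infer that dropping the PP sets is what makes these subjects count as responders. The documents do not support that: the protocol had already made the FA set primary, and its definition never had a serostatus or therapy condition. What was lost is a supportive analysis, and SAP 12 declares and explains the loss. This stands, and it limits the point to a missing check.

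A reader might also infer that the PP sets would have handled outside rabies vaccination throughout follow-up, or that late persistence is the most exposed result. Neither is established.
- Exclusion criterion 3 concerns rabies vaccine before the trial vaccine. Criterion 8 concerns immunoglobulins and blood products in the three months before a trial dose. PP1 and PP2 were built on results to Day 57 and Day 91. None of these clearly reaches late post-exposure treatment.
- Protocol 8.9 mentions only safety follow-up after such vaccination, and section 7.1 makes immunogenicity sampling discretionary once further doses are stopped. Later VNT results are possible, not certain.
- Month 18 and 24 VNTs are taken only if specific IgG was detectable at Month 6, or at Day 91 if the Month 6 sample is unavailable. A subject without IgG then who is vaccinated elsewhere later would not be sampled.

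Safeguards remain. Criteria 3 and 4 exclude prior rabies vaccination and planned travel to risk areas, and section 8.10 provides individual case review. Tables 14.2.1.1 and 14.2.1.2 have a Day 1 row, listing 16.2.6.1 flags each titer against 0.5 IU/ml, and listing 16.2.4.3 dates other vaccinations. These lower the likelihood and make a case visible, but they do not correct the later rows. The data review meeting could act, but under no written rule. The note to listing 16.2.3.1 allows an FA exclusion that SAP 8 does not.

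Finally, SAP 10 refers details of immunogenicity data analysis to the immunomonitoring analysis plan, which was not available for this review and might contain a rule.

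**Conclusion.** The point holds as a gap in the SAP: after section 12, no planned analysis separates titers that CV7202 did not cause, and section 10.2 as written counts them. It is conditional. The documents show no affected subject and give no expected number, and with none the tables are unaffected. No hypothesis test is involved, because the trial is descriptive.

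For one affected subject, the size is 5.4 to 12.5 points in a regimen of 8 and 2.9 to 6.3 points in a group of 16, as the others' response falls from about half to none. It would be tempting to quote 12.5 points as the general effect at n = 8. That figure applies only when nobody else responds, or when the subject is assumed to be a certain non-responder who stays in the denominator, which the documents do not show. The exact intervals with and without the subject overlap heavily, so the issue is how individual cells are read.

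**What to change.** Keep the FA set and its tables, and leave the PP sets out. Then:

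1. In SAP 10.2 and 10.3.1, state that VNT and immunoglobulin results obtained after any non-trial rabies vaccine, immunoglobulin or blood product are set to missing in summaries and flagged in the listings.
2. Add a supportive version of tables 14.2.1.1 to 14.2.1.4 restricted to subjects with Day 1 VNT below 0.5 IU/ml. Protocol 10.2 gives no titer that defines pre-existing immunity, so the SAP must state one. This choice matches the endpoint's own cut-off.
3. Reconcile the note to listing 16.2.3.1 with the FA definition in SAP 8.
4. Declare these rules in SAP 12, and check them against the immunomonitoring analysis plan.

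The Day 1 titers and dated concomitant vaccinations and medications are already collected, so the cost is SAP wording, two programming filters and one extra set of tables. A denominator may fall by one in an affected group. If the rules are added after the SAP is final, SAP 6 requires the output to be labelled post hoc.

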13. REFERENCES

Not applicable

14. APPENDICES

Appendix A: Presentation of Data and Programming Specifications

General

- Specialized text styles, such as bold, italics, borders, shading, superscripted, and subscripted text will not be used in tables, figures, and data listings unless they add significant value to the table, figure, or data listing.
- Only standard keyboard characters are to be used in tables and data listings.
- Special characters, such as nonprintable control characters, printer specific, or font specific characters, will not be used on a table, figure, or data listing.
- Hexadecimal character representations are allowed (eg, μ , α , β).
- All footnotes will be left justified and at the bottom of a page. Footnotes should be used sparingly and must add value to the table, figure, or data listing.

Tables

- Formal organization of tabulations may be changed during programming, if appropriate, eg, tables for the different variables may be combined into a single table, or tables with more than 1 variable may be split into several tables.
- Means and medians will be presented to 1 more decimal place than the raw data. Standard deviations will be presented to 2 more decimal places than the raw data. Minimums and maximums will be reported with the same number of decimal places as the raw data.
- Percentages will be presented to the tenth place.
- For frequency counts of categorical variables, categories whose counts are zero will be displayed for the sake of completeness. For example, if none of the subjects discontinue due to “lost to follow-up,” this reason will be included in the table with a count of 0. Categories with zero counts will not have zero percentages displayed.
- The last footnotes will be
 - “PROGRAM SOURCE: ...\\xx.sas, DATA CUT OFF DATE: DDMMYYYY, RUN DATE: DDMMYY hh:mm”, where data cut-off date is the datestamp of the data snapshot used.

Figures

- Legends will be used for all figures with more than 1 variable or item displayed. Figures will be in black and white but can be in color to add value to the clarity and readability of a figure. Lines should be wide enough to see the line after being copied.
- The last footnotes will be
 - “PROGRAM SOURCE: ...\\xx.sas, DATA CUT OFF DATE: DDMMYYYY, RUN DATE: DDMMYY hh:mm”, where data cut-off date is the datestamp of the data snapshot used.

Listings

- Formal organization of the listings may be changed during programming, if appropriate, eg, additional variables may be included, change in the column order, or the listing may be split into multiple parts due to space constraints.
- If not otherwise specified, all data listings will be sorted by sequence/treatment, center, subject number, visit, and date/time, as appropriate.
- All date values will be presented in a SAS date (eg, 29AUG2001) format.
- All observed time values will be presented using a 24-hour clock HH:MM:SS format (eg, 01:35:45 or 11:26). Seconds will only be reported if they were measured as part of the study.
- The last footnote will be
 - "PROGRAM SOURCE: ...\\xx.sas, DATA CUT OFF DATE: DDMMYYYY, RUN DATE: DDMMYY hh:mm", where data cut-off date is the datestamp of the data snapshot used.

Standard Calculations

Variables requiring calculation will be derived using the following formulas:

- **Days** – A duration expressed in days between 1 date (date1) and another later date (date2) is calculated using the formulas noted below:
duration in days = date2 – date1 + 1
- **Change from baseline** – Change from baseline will be calculated as:
Change = postbaseline value – baseline value.

Appendix B: SAS Programming QC requirements

All items must be completed to meet department programming validation standards as described in **WI-SOP-0205-003 QC Requirements**.

Appendix C: List of Tables, Figures, and Listings

The following proposal for sections 14 and 16.2 is completed according to ICH E3 guidelines. The ICH heading numbers and description are in **bold**.

Index of section 14

Table Number	Table Title	Analysis Set	Comment
14	TABLES, FIGURES, AND GRAPHS REFERRED TO BUT NOT INCLUDED IN THE TEXT		
14.1	Demographic Data		
14.1.1	Subject Disposition by Dosage/Vaccine	All Subjects	
14.1.2	Subject Disposition by Dosage/Vaccine and Treatment Group	All Subjects	
14.1.3	Subject Number by Country and Site	Safety Analysis Set	
14.1.4	Demographic Characteristics		
14.1.4.1	Demographic Characteristics by Dosage/Vaccine	Safety Analysis Set	
14.1.4.2	Demographic Characteristics by Dosage/Vaccine and Treatment Group	Safety Analysis Set	
14.1.4.3	Demographic Characteristics by Dosage/Vaccine	Full Analysis Set	
14.1.4.4	Demographic Characteristics by Dosage/Vaccine and Treatment Group	Full Analysis Set	
14.1.5	Baseline Characteristics		
14.1.5.1	Baseline Characteristics by Dosage/Vaccine	Safety Analysis Set	
14.1.5.2	Baseline Characteristics by Dosage/Vaccine and Treatment Group	Safety Analysis Set	
14.1.5.3	Baseline Characteristics by Dosage/Vaccine	Full Analysis Set	
14.1.5.4	Baseline Characteristics by Dosage/Vaccine and Treatment Group	Full Analysis Set	
14.1.6	Concomitant Medications/Vaccinations by Dosage/Vaccine	Safety Analysis Set	
14.2	Immunogenicity Data		
14.2.1	Secondary Immunogenicity Endpoint - Rabies Specific VNTs		
14.2.1.1	Rabies Specific VNTs ≥ 0.5 IU/ml by Dosage/Vaccine	Full Analysis Set	
14.2.1.2	Rabies Specific VNTs ≥ 0.5 IU/ml by Dosage/Vaccine and Treatment Group	Full Analysis Set	
14.2.1.3	Rabies Specific VNTs (IU/mL) by Dosage/Vaccine	Full Analysis Set	
14.2.1.4	Rabies Specific VNTs (IU/mL) by Dosage/Vaccine and Treatment Group	Full Analysis Set	

Table Number	Table Title	Analysis Set	Comment
14.2.2	Exploratory Immunogenicity Endpoints - Immunoglobulin		
14.2.2.1	RABV-G Specific Levels of IgM		
14.2.2.1.1	RABV-G Specific Levels of IgM ≥ 780 U/ml by Dosage/Vaccine	Full Analysis Set	
14.2.2.1.2	RABV-G Specific Levels of IgM ≥ 780 U/ml by Dosage/Vaccine and Treatment Group	Full Analysis Set	
14.2.2.1.3	RABV-G Specific Levels of IgM (U/mL) by Dosage/Vaccine	Full Analysis Set	
14.2.2.1.4	RABV-G Specific Levels of IgM (U/mL) by Dosage/Vaccine and Treatment Group	Full Analysis Set	
14.2.2.2	RABV-G Specific Levels of IgA		
14.2.2.2.1	RABV-G Specific Levels of IgA ≥ 195.5 U/ml by Dosage/Vaccine	Full Analysis Set	
14.2.2.2.2	RABV-G Specific Levels of IgA ≥ 195.5 U/ml by Dosage/Vaccine and Treatment Group	Full Analysis Set	
14.2.2.2.3	RABV-G Specific Levels of IgA (U/mL) by Dosage/VaccineVisit	Full Analysis Set	
14.2.2.2.4	RABV-G Specific Levels of IgA (U/mL) by Dosage/Vaccine and Treatment Group	Full Analysis Set	
14.2.2.3	RABV-G Specific Levels of IgG		
14.2.2.3.1	RABV-G Specific Levels of IgG ≥ 780 U/ml by Dosage/Vaccine	Full Analysis Set	
14.2.2.3.2	RABV-G Specific Levels of IgG ≥ 780 U/ml by Dosage/Vaccine and Treatment Group	Full Analysis Set	
14.2.2.3.3	RABV-G Specific Levels of IgG by Dosage/Vaccine	Full Analysis Set	
14.2.2.3.4	RABV-G Specific Levels of IgG by Dosage/Vaccine and Treatment Group	Full Analysis Set	
14.2.3	Exploratory Immunogenicity Endpoints		
14.2.3.1	Cellular Immune Response by Dosage/Vaccine	Full Analysis Set	
14.2.3.2	Cellular Immune Response by Dosage/Vaccine and Treatment Group	Full Analysis Set	
14.2.3.3	Cytokine Assessment by Dosage/Vaccine	Full Analysis Set	
14.2.3.4	Cytokine Assessment by Dosage/Vaccine and Treatment Group	Full Analysis Set	
14.3	Safety Data		
14.3.1	Displays of Adverse Events		
14.3.1.1	Solicited Adverse Events		
14.3.1.1.1	Summaries of Solicited Adverse Events		

Table Number	Table Title	Analysis Set	Comment
14.3.1.1.1.1	Summary of Solicited Adverse Events Within 7 Days After Any Dose	Safety Analysis Set	
14.3.1.1.1.2	Summary of Solicited Adverse Events Within 7 Days Post Dose 1	Safety Analysis Set	
14.3.1.1.1.3	Summary of Solicited Adverse Events Within 7 Days Post Dose 2	Safety Analysis Set	
14.3.1.1.1.4	Summary of Solicited Adverse Events Within 7 Days Post Dose 3	Safety Analysis Set	
14.3.1.1.1.5	Local Solicited Adverse Events Within 7 Days After any Dose	Safety Analysis Set	
14.3.1.1.1.6	Local Solicited Adverse Events Within 7 Days Post Dose 1	Safety Analysis Set	
14.3.1.1.1.7	Local Solicited Adverse Events Within 7 Days Post Dose 2	Safety Analysis Set	
14.3.1.1.1.8	Local Solicited Adverse Events Within 7 Days Post Dose 3	Safety Analysis Set	
14.3.1.1.1.9	Systemic Solicited Adverse Events Within 7 Days After any Dose	Safety Analysis Set	
14.3.1.1.1.10	Systemic Solicited Adverse Events Within 7 Days Post Dose 1	Safety Analysis Set	
14.3.1.1.1.11	Systemic Solicited Adverse Events Within 7 Days Post Dose 2	Safety Analysis Set	
14.3.1.1.1.12	Systemic Solicited Adverse Events Within 7 Days Post Dose 3	Safety Analysis Set	
14.3.1.1.1.13	Related Systemic Solicited Adverse Events Within 7 Days After any Dose	Safety Analysis Set	
14.3.1.1.1.14	Related Systemic Solicited Adverse Events Within 7 Days Post Dose 1	Safety Analysis Set	
14.3.1.1.1.15	Related Systemic Solicited Adverse Events Within 7 Days Post Dose 2	Safety Analysis Set	
14.3.1.1.1.16	Related Systemic Solicited Adverse Events Within 7 Days Post Dose 3	Safety Analysis Set	
14.3.1.1.2	Number of Days of Local Solicited Adverse Events		
14.3.1.1.2.1	Number of Days of Local Solicited Adverse Events Post Dose 1	Safety Analysis Set	
14.3.1.1.2.2	Number of Days of Local Solicited Adverse Events Post Dose 2	Safety Analysis Set	
14.3.1.1.2.3	Number of Days of Local Solicited Adverse Events Post Dose 3	Safety Analysis Set	
14.3.1.1.2.4	Number of Days of Grade 3 Local Solicited Adverse Events Post Dose 1	Safety Analysis Set	
14.3.1.1.2.5	Number of Days of Grade 3 Local Solicited Adverse Events Post Dose 2	Safety Analysis Set	
14.3.1.1.2.6	Number of Days of Grade 3 Local Solicited Adverse Events Post Dose 3	Safety Analysis Set	
14.3.1.1.2.7	Number of Days of Systemic Solicited Adverse Events Post Dose 1	Safety Analysis Set	
14.3.1.1.2.8	Number of Days of Systemic Solicited Adverse Events Post Dose 2	Safety Analysis Set	
14.3.1.1.2.9	Number of Days of Systemic Solicited Adverse Events Post Dose 3	Safety Analysis Set	
14.3.1.1.2.10	Number of Days of Grade 3 Systemic Solicited Adverse Events Post Dose 1	Safety Analysis Set	
14.3.1.1.2.11	Number of Days of Grade 3 Systemic Solicited Adverse Events Post Dose 2	Safety Analysis Set	
14.3.1.1.2.12	Number of Days of Grade 3 Systemic Solicited Adverse Events Post Dose 3	Safety Analysis Set	
14.3.1.1.3	Daily Summaries of Solicited Adverse Events		

Table Number	Table Title	Analysis Set	Comment
14.3.1.1.3.1	Daily Summary of Local Solicited Adverse Events Post Dose 1	Safety Analysis Set	
14.3.1.1.3.2	Daily Summary of Local Solicited Adverse Events Post Dose 2	Safety Analysis Set	
14.3.1.1.3.3	Daily Summary of Local Solicited Adverse Events Post Dose 3	Safety Analysis Set	
14.3.1.1.3.4	Daily Summary of Systemic Solicited Adverse Events Post Dose 1	Safety Analysis Set	
14.3.1.1.3.5	Daily Summary of Systemic Solicited Adverse Events Post Dose 2	Safety Analysis Set	
14.3.1.1.3.6	Daily Summary of Systemic Solicited Adverse Events Post Dose 3	Safety Analysis Set	
14.3.1.1.4	Days of First Onset of Solicited Advers Events		
14.3.1.1.4.1	Day of First Onset of Solicited Adverse Events Post Dose 1	Safety Analysis Set	
14.3.1.1.4.2	Day of First Onset of Solicited Adverse Events Post Dose 2	Safety Analysis Set	
14.3.1.1.4.3	Day of First Onset of Solicited Adverse Events Post Dose 3	Safety Analysis Set	
14.3.1.1.4.4	Day of First Onset of Local Solicited Adverse Events Post Dose 1	Safety Analysis Set	
14.3.1.1.4.5	Day of First Onset of Local Solicited Adverse Events Post Dose 2	Safety Analysis Set	
14.3.1.1.4.6	Day of First Onset of Local Solicited Adverse Events Post Dose 3	Safety Analysis Set	
14.3.1.1.4.7	Day of First Onset of Systemic Solicited Adverse Events Post Dose 1	Safety Analysis Set	
14.3.1.1.4.8	Day of First Onset of Systemic Solicited Adverse Events Post Dose 2	Safety Analysis Set	
14.3.1.1.4.9	Day of First Onset of Systemic Solicited Adverse Events Post Dose 3	Safety Analysis Set	
14.3.1.1.4.10	Day of First Onset of Related Systemic Solicited Adverse Events Post Dose 1	Safety Analysis Set	
14.3.1.1.4.11	Day of First Onset of Related Systemic Solicited Adverse Events Post Dose 2	Safety Analysis Set	
14.3.1.1.4.12	Day of First Onset of Related Systemic Solicited Adverse Events Post Dose 3	Safety Analysis Set	
14.3.1.2	Unsolicited Adverse Events Within 28 Days		
14.3.1.2.1	Overall Summary of Unsolicited Adverse Events Within 28 Days After any Dose	Safety Analysis Set	
14.3.1.2.2	Overall Summary of Unsolicited Adverse Events Within 28 Days Post Dose 1	Safety Analysis Set	
14.3.1.2.3	Overall Summary of Unsolicited Adverse Events Within 28 Days Post Dose 2 CV7202 or Dose 3 Rabipur	Safety Analysis Set	
14.3.1.2.4	Summary of Unsolicited Adverse Events Within 28 Days by Maximum Intensity (Grade) After any Dose	Safety Analysis Set	
14.3.1.2.5	Unsolicited Adverse Events Within 28 Days After any Dose	Safety Analysis Set	
14.3.1.2.6	Unsolicited Adverse Events Within 28 Days Post Dose 1	Safety Analysis Set	

Table Number	Table Title	Analysis Set	Comment
14.3.1.2.7	Unsolicited Adverse Events Within 28 Days Post Dose 2 CV7202 or Dose 3 Rabipur	Safety Analysis Set	
14.3.1.3	Unsolicited Adverse Events for the Duration of the Trial	Safety Analysis Set	
14.3.1.3.1	Overall Summary of Unsolicited Adverse Events for the Duration of the Trial after Any Dose	Safety Analysis Set	
14.3.1.3.2	Summary of Unsolicited Adverse Events for the Duration of the Trial by Maximum Intensity (Grade) after Any Dose	Safety Analysis Set	
14.3.1.3.3	Unsolicited Adverse Events for the Duration of the Trial after Any Dose	Safety Analysis Set	
14.3.1.3.4	Unsolicited Adverse Events for the Duration of the Trial Post Dose 1	Safety Analysis Set	
14.3.1.3.5	Unsolicited Adverse Events for the Duration of the Trial Post Dose 2 CV7202 or Dose 3 Rabipur	Safety Analysis Set	
14.3.2	Listings of Deaths, Other Serious and Significant Adverse Events	Safety Analysis Set	Layout analogous to section 16.2 AE listings
14.3.3	Narratives of Deaths, Other Serious and Certain Other Significant Adverse Events	Safety Analysis Set	This is a cross-reference to section 12.3.2 of the CSR
14.3.4	Abnormal Laboratory Value Listing (Each Subject)	Safety Analysis Set	Layout analogous to section 16.2 lab listings
14.3.5	Vaccination Site Reactogenicity Investigator Assessment	Safety Analysis Set	
14.3.5.1	Vaccination Site Reactogenicity Investigator Assessment Overview	Safety Analysis Set	
14.3.5.2	Vaccination Site Reactogenicity Investigator Assessment Overview by Treatment Group	Safety Analysis Set	
14.3.5.3	Vaccination Site Reactogenicity Investigator Assessment	Safety Analysis Set	
14.3.5.4	Vaccination Site Reactogenicity Investigator Assessment by Treatment Group	Safety Analysis Set	
14.3.6	Extent of Exposure	Safety Analysis Set	
14.3.7	Other Safety Data	Safety Analysis Set	
14.3.7.1	Weight and BMI	Safety Analysis Set	
14.3.7.2	Vital Signs	Safety Analysis Set	

Table Number	Table Title	Analysis Set	Comment
14.3.7.3	Safety Laboratory Data		
14.3.7.3.1	Hematology	Safety Analysis Set	
14.3.7.3.2	Biochemistry	Safety Analysis Set	
14.3.7.3.3	Coagulation	Safety Analysis Set	

Index of section 16.2

ICH Listing Number	Listing Title	Analysis Set
16.2	SUBJECT DATA LISTINGS	
16.2.1	Discontinued Subjects	
16.2.1.1	Subject Disposition	All Subjects
16.2.1.2	Discontinued Subjects	All Subjects
16.2.2	Protocol Deviations	
16.2.2.1	Protocol Deviations	All Subjects
16.2.2.2	Eligibility and Subjects not Fulfilling any Inclusion/Exclusion Criteria	All Subjects
16.2.3	Subjects Excluded From the Efficacy/Immunogenicity Analysis	
16.2.3.1	Subjects Excluded From Analysis	All Subjects
16.2.4	Demographic data	
16.2.4.1	Demographics and Baseline Characteristics	Safety Analysis Set
16.2.4.2	Medical History	Safety Analysis Set
16.2.4.3	Prior and Concomitant Medications/Vaccinations	Safety Analysis Set
16.2.5	Vaccination Data	
16.2.6	Immunogenicity Data	
16.2.6.1	VNTs	Full Analysis Set
16.2.6.2	RABV-G specific Immunoglobulin (ELISA)	Full Analysis Set
16.2.6.3	Cellular Immune Response and Leucocytes Phenotyping (PBMCs)	Full Analysis Set
16.2.6.4	Cytokine Assessment	Full Analysis Set
16.2.7	Adverse Event and Vaccination Site Reactogenicity Assessment Listings	
16.2.7.1	Unsolicited Adverse Events	
16.2.7.1.1	Unsolicited Adverse Events - CRF Entries	Safety Analysis Set
16.2.7.1.2	Unsolicited Adverse Events - MedDRA Coding	Safety Analysis Set
16.2.7.1.3	Serious Unsolicited Adverse Events	Safety Analysis Set
16.2.7.1.4	Unsolicited Adverse Events Leading to Trial or Vaccine Withdrawal	Safety Analysis Set
16.2.7.1.5	Deaths	Safety Analysis Set
16.2.7.2	Solicited Adverse Events	
16.2.7.2.1	Local Solicited Adverse Events	Safety Analysis Set

ICH Listing Number	Listing Title	Analysis Set
16.2.7.2.2	Systemic Solicited Adverse Events	Safety Analysis Set
16.2.7.3	Vaccination Site Reactogenicity Assessment (by Investigator)	Safety Analysis Set
16.2.8	Listing of Individual Laboratory Measurements by Subject	
16.2.8.1	Hematology	Safety Analysis Set
16.2.8.2	Biochemistry	Safety Analysis Set
16.2.8.3	Coagulation	Safety Analysis Set
16.2.8.4	Pregnancy Test Results	Safety Analysis Set
16.2.9	Other Data	
16.2.9.1	Physical Examination, Weight, BMI	Safety Analysis Set
16.2.9.2	Vital Signs	Safety Analysis Set
16.2.9.3	Electrocardiogram	Safety Analysis Set
16.2.10	Visit and Diary Information	Safety Analysis Set

